## **8. APPENDIX 2: MAJOR PROTOCOL DEVIATIONS**

Major Protocol Deviations are defined as any intentional or unintentional change from the IRB-approved protocol that adversely affects the risk/benefit ratio of the study; the rights, safety, or welfare of the participants or others; or the integrity of the study and interferes with evaluation of efficacy or safety of the study drug. The list of Major Protocol Deviations is provided below.

- IRB/IEC approved informed consent not signed and dated prior to initiating any study specific procedures,
- Inclusion/exclusion (I/E) criteria not verified prior to patient enrollment or not met, and patient enrolled despite not meeting I/E criteria
- Misrandomization
- Overdose,
- Use of IP where medication usability is compromised (i.e. expired study drug, study drug that has experienced temperature excursion and has not been approved for use by Sponsor)
- Patient taking/receiving any disallowed concomitant medication or therapy
- Inadequate reporting or documentation of serious adverse events (SAEs),
- Evidence of serious misconduct at the site

## **Purpose**

The purpose of this document is to define additional, pre-defined supportive efficacy analyses of the primary efficacy endpoint by additional subgroups of interest for study ISIS 681257-CS6. In addition, this document slightly redefines treatment compliance to better capture partial doses received.

## **Additional Subgroups**

In addition to the subgroups defined in the final statistical analysis plan (SAP v1.0) dated 12 April 2018, the following subgroups are defined:

### Baseline Lp(a)

The analyses by baseline Lp(a) will be categorized by quartiles, as well as >70 mg/dL versus ≤70 mg/dL.

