#### 1.2.5. Efficacy and Safety Parameters

##### 1.2.5.1. Primary Efficacy Parameters

The primary efficacy endpoint is the percent change in Lp(a) from baseline at the primary analysis time point achieved by ISIS 681257 compared to placebo.

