### **3.4. Baseline Definitions**

Baseline for Lp(a), LDL-C, apoB, OxPL-apo(a), OxPL-apoB, and other lipid measurements will be defined as the pre-dose measurement on Day 1 or closest to Day 1, prior to administration of Study Drug. The baseline for platelet count is defined as the average of all platelet count data points prior to the first dose of the study drug. The baseline for other measurements is defined as the last non-missing assessment prior to the first dose of study drug.

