## **4. STUDY ANALYSES**

Treatment groups are ISIS 681257 treatment groups and pooled placebo group. ISIS 681257 treatment groups include:

ISIS 681257 20 mg (Every 4 weeks)

ISIS 681257 40 mg (Every 4 weeks)

ISIS 681257 60 mg (Every 4 weeks)

ISIS 681257 20 mg (Every 2 weeks)

ISIS 681257 20 mg (Every week)

Within cohort comparisons between patients receiving ISIS 681257 and patients receiving placebo will be performed for selected safety endpoints, as appropriate.

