#### **4.3.1. Analysis of the Primary Efficacy Endpoint**

As described in Section 1.2.5, the primary efficacy endpoint is the percent change in fasting Lp(a) from baseline at the primary analysis time point (Week 25 for patients in Cohorts A-C; Week 27 for patients in Cohorts D-E) achieved by ISIS 681257 compared to placebo.

The percent change from baseline in Lp(a) will be analyzed using an ANCOVA model with treatment group as factors and log-transformed baseline Lp(a) as covariate. The ANCOVA model will use  $\log(Y/X)$  as dependent variable, where Y is the post-baseline value of Lp(a) and X is the baseline value of Lp(a). The model will provide an estimate of the log ratio, which will then be converted back to the original ratio scale. The percent change from baseline will then be estimated based on the estimated ratio. Patients with missing primary endpoint will have their fasting Lp(a) value imputed using the multiple imputation method described in Section 3.10.1.

The primary endpoint will be compared between ISIS 681257 treatment groups and the pooled placebo group for each of the 100 imputed datasets. The estimates from the 100 fitted models will be combined to provide an overall estimate, with corresponding CIs and p-value (Little and Rubin, 2002). Results from the ANCOVA model will be tabulated by ISIS 681257 treatment groups compared to the pooled placebo group.

Mean (SD) percent change over time in fasting Lp(a) will be plotted by ISIS 681257 treatment group and pooled placebo group, until there are fewer than 10% of the FAS/PPS population at a given visit. Waterfall plots of by-patient percent changes from baseline to the primary analysis time point will also be provided.

The primary efficacy analysis will take place after the last patient has completed the primary analysis time point, and the database has been locked.

All primary efficacy data will be provided in data listings.

The primary efficacy analysis will be done using the FAS population.

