### **Supportive Efficacy Analyses**

In addition to those described in the SAP version 1.0, the change and percent change from baseline in Lp(a) over time will be tabulated by treatment group for all subgroups defined above. Descriptive statistics will be presented (n, mean, std, Q1, median, Q3, min, and max) for all visits. Data will be reported as collected; missing data will not be imputed.

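### The addendum tabulates percent change in Lp(a) within strata of the same baseline reading and plans no placebo-adjusted estimate, so regression to the mean could be misread as a larger effect at high baseline

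*SAP*

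**What the plan says.** The SAP addendum describes its analyses as "additional, pre-defined supportive efficacy analyses of the primary efficacy endpoint by additional subgroups of interest". Under Baseline Lp(a) it sets the strata: "The analyses by baseline Lp(a) will be categorized by quartiles, as well as >70 mg/dL versus ≤70 mg/dL". Under Supportive Efficacy Analyses it says that "the change and percent change from baseline in Lp(a) over time will be tabulated by treatment group for all subgroups defined above", and that "Descriptive statistics will be presented (n, mean, std, Q1, median, Q3, min, and max) for all visits". Missing values are not imputed there. No contrast with placebo, confidence interval, baseline adjustment or interaction is specified for these strata.

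Three parts of the main SAP bear on this:

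- Section 3.4: baseline Lp(a) "will be defined as the pre-dose measurement on Day 1 or closest to Day 1, prior to administration of Study Drug". It is one reading. The same section averages all pre-dose values for platelets.
- Section 1.2.5.1: the primary endpoint is "the percent change in Lp(a) from baseline at the primary analysis time point achieved by ISIS 681257 compared to placebo". Section 4.3.1 estimates it on the log-ratio scale with an "ANCOVA model with treatment group as factors and log-transformed baseline Lp(a) as covariate".
- Section 4: "Treatment groups are ISIS 681257 treatment groups and pooled placebo group". Each addendum table will therefore carry a pooled placebo column.

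**The concern.** The Day 1 reading decides a patient's stratum and is also the denominator of the percent change. Any noise in it enters both, in opposite directions. Readings that are low by chance tend to rise afterwards and readings that are high by chance tend to fall, with or without drug. The statin, niacin and PCSK9 inhibitor subgroups in the same addendum have no such built-in link. The 70 mg/dL cut adds to the problem, because entry requires at least 60 mg/dL and the lower stratum sits just above the entry limit.

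The tables are presented as analyses of an endpoint that is a comparison with placebo, but they stop at within-arm summaries. Whether the effect depends on baseline Lp(a) is the natural question to ask of them, and they give no estimate that answers it free of this artefact.

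**Working it through.** **Planning figures (SAP section 3.1).** SD 20 points, 30% versus 10% reduction, 23 per group, two-sided 5%. A two-sample t-test gives power 0.912, which agrees with the stated 90% or so. The planned numbers are 45 patients per active group and 5 × 9 = 45 on pooled placebo.

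**Log-scale SD of change.** With a placebo mean ratio of 0.9 and SD of 0.20: √ln(1 + (20/90)²) = 0.2195, variance 0.0482.

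**Within-patient noise (assumption).** The SAP does not give it. If a share *f* of the variance of change is noise, split equally between two readings, then sw² = *f* × 0.0482 / 2. At *f* = 100%, sw = 0.155, which is a ceiling.

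**Regression to the mean in the extreme quartiles.** For a roughly normal log baseline with SD sB (also not in the SAP), the mean of the top quartile lies 1.271 SD above the centre. The spurious log change is r = 1.271 × sw² / sB, negative in the top quartile (Q4) and positive in the bottom (Q1). The false gap in percent points is 100 × (e^r − e^−r).

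| Noise share *f* | sw | Gap, sB 0.3 | Gap, sB 0.7 |
|---|---|---|---|
| 10% | 0.049 | 2.0 | 0.9 |
| 25% | 0.078 | 5.1 | 2.2 |
| 50% | 0.110 | 10.2 | 4.4 |
| 100% | 0.155 | 20.5 | 8.8 |

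Example, *f* = 100% and sB = 0.3: r = 1.271 × 0.0241 / 0.3 = 0.102, so +10.8% in Q1 and −9.7% in Q4.

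**Simulation with the entry cut.** Assumptions: no drug effect, screening value at least 150 nmol/L (60 mg/dL × 2.5), population median 225 nmol/L, between-patient log SD 0.3 to 0.7 before the cut. The Q1–Q4 gap is about 1 to 2.5 points at *f* = 10% and about 3 to 21 points over *f* = 25–100%. For ≤70 versus >70 mg/dL the gap is about 4 to 17 points over *f* = 25–100%. Gaps are the figures to use here. The quartile levels themselves carry about +2.4% from the skew of an arithmetic mean percent change (e^(0.0482/2) − 1), which is not regression to the mean.

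**What a table would show under a constant effect.** True ratios 0.7 (active) and 0.9 (placebo) at every baseline, from the formula above with sB = 0.4:

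| sw | Active Q1 | Active Q4 | Placebo Q1 | Placebo Q4 |
|---|---|---|---|---|
| 0.10 | −27.7% | −32.2% | −7.1% | −12.8% |
| 0.155 | −24.4% | −35.2% | −2.8% | −16.6% |

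Both columns slope the same way.

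**Does a placebo contrast remove it?** In a simulation with the same true ratios and entry at 60 mg/dL, the active-to-placebo ratio was 0.777–0.778 in every quartile for sw of 0.05, 0.10 and 0.156 (true value 0.7/0.9 = 0.778). Subtracting percent points is slightly less clean: −22.1 in Q1 against −19.5 in Q4 at sw 0.156.

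**Precision.** Each quartile-by-arm cell has 45/4 ≈ 11 patients. SE of an arm mean: 20/√11.25 = 6.0 points. SE of an active–placebo difference: 20 × √(2/11.25) = 8.4 points. 95% half-width: 1.96 × 8.43 ≈ 16.5 points.

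**The case against.** The strongest reply is that the control is already in the table. Pooled placebo is one of the treatment groups, so each stratum has a concurrent randomised placebo column with the same gradient, and a reader who compares columns can see it. This stands. A reader might infer that the tables *will* show a false drug effect; the SAP does not support that. The misreading arises only if the active columns are read alone.

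Second, the tables are supportive and descriptive. The addendum attaches no test or decision to them, and the primary ANCOVA adjusts for log baseline. This also stands. The repeated-measures model in section 4.3.3 includes baseline and visit-by-baseline terms, but no treatment-by-baseline term, so it does not answer the question either.

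Third, the addendum adds to SAP version 1.0, and section 3.8 already plans subgroup analyses of the primary endpoint, so the new strata might inherit the primary model. That is unclear: section 3.8 lists only age and gender, and the addendum spells out only descriptive output.

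Fourth, the size rests on assumptions. At low within-patient noise the gap is 1 to 2 points, negligible beside a cell SE of 6 points. This stands, and it is why no single figure can be claimed.

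What remains is that subtracting columns by eye, with about 11 patients per cell and no interval, is a poor substitute for an estimate that costs one model.

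**Conclusion.** The concern holds as a minor point. The addendum stratifies on the single reading that is also the denominator of its outcome, and it specifies no estimate that removes the resulting regression to the mean. A gradient across baseline strata is expected in all columns, placebo included, even if the drug effect is the same at every baseline.

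Its size is not fixed by the documents. It is about 1 point between extreme quartiles if 10% of the variance of change is within-patient noise, and about 20 points if all of it is. That assumes a between-patient log SD of 0.3 to 0.7 and a log SD of change of 0.22, derived from the SAP's 20-point SD. The upper end equals the 20-point planning effect, but it is a ceiling and not an expected value. The primary efficacy result is not in question.

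**What to change.** Keep the descriptive tables and add one paragraph to the addendum:

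1. At the primary analysis time point (Week 25/27), fit the existing ANCOVA on log(Y/X) with an added interaction between treatment and continuous log baseline Lp(a). Report this as the main result on baseline dependence.
2. For each baseline stratum, report the placebo-adjusted percent change with its 95% CI, back-transformed from the log-ratio scale.
3. State that any claim that the effect depends on baseline Lp(a) rests on items 1 and 2, and not on within-arm percent changes.

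On the log-ratio scale regression to the mean is the same in active and placebo patients, so it cancels. The cost is a paragraph of text and one extra model on data already collected. The drawback is precision: stratum intervals of about ±16 points cannot settle much, which is why the continuous interaction should lead.

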### Intensity of Statin Therapy

Intensity of statin therapy will be categorized as either High or Moderate/Low, by the use of the following concomitant medication while on-treatment:

- High-intensity: atorvastatin (40-80 mg/day), rosuvastatin (20-40 mg/day), and simvastatin (>40 mg/day). The medication names to be used are the following:
  - ATORVASTATIN
  - ROSUVASTATIN
  - SIMVASTATIN
  
- Moderate/Low-intensity: atorvastatin (<40 mg/day), rosuvastatin (<20 mg/day), simvastatin (≤40 mg/day), and any other statin medication will be considered low levels. The following medication names, in addition to those above, are to be used:
  - FLUVASTATIN
  - LOVASTATIN
  - PITAVASTATIN
  - PRAVASTATIN
  - INEGY
  - ZETITOR

Patients who do not take any statin medication will also be classified as Moderate/Low-intensity.

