## 1.2. Study Design

### 1.2.1. Synopsis of Study Design

This is a multicenter, randomized, double-blind, placebo-controlled, dose-ranging study. ISIS 681257 (or placebo) will be administered subcutaneously (SC) every week, every 2 weeks, or every 4 weeks, depending on cohort assignment, for up to 52 weekly doses, up to 26 every 2-week doses, or up to 13 every 4-week doses. Minimum treatment duration is 6 months, maximum treatment duration is 12 months.

The primary analysis time point is at Week 25 for patients who received every 4-week dosing (Cohorts A-C) and at Week 27 for patients who received 2-week or weekly dosing (Cohorts D and E). For patients continuing treatment beyond the primary analysis time point additional supportive efficacy analysis (to evaluate whether the treatment effect is maintained) and safety analysis (for the purpose of dose(s) selection) will be repeated at the completion of Study Drug treatment. A description of each cohort is presented in [Table 1](#).

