**Table 1: Study Drug Dosing Information**

Cohort	Treatment	Volume to Administer/Dose	# Doses	Total ISIS 681257
A	20 mg ISIS 651257 or placebo (every 4 weeks)	0.2 mL	≤ 13	≤ 260 mg
B	40 mg ISIS 651257 or placebo (every 4 weeks)	0.4 mL	≤ 13	≤ 520 mg
C	60 mg ISIS 651257 or placebo (every 4 weeks)	0.6 mL	≤ 13	≤ 780 mg
D	20 mg ISIS 651257 or placebo (every 2 weeks)	0.2 mL	≤ 26	≤ 520 mg
E	20 mg ISIS 651257 or placebo (every week)	0.2 mL	≤ 52	≤ 1040 mg

The treatment portion of the study will be complete when the last enrolled patient reaches 6 months of exposure. All patients still on treatment will have their last dose taken as scheduled, and they will enter a 16-week post-treatment follow-up period at one dosing interval post last dose. Accordingly, for each treatment cohort treatment period is defined as the time from the first dose through one dosing interval post last dose.

Patients  $\geq 18$  and  $\leq 80$  years old with elevated plasma Lp(a) levels ( $\geq 60$  mg/dL ) and a clinical diagnosis of CVD are eligible for enrollment upon meeting the study specific eligibility criteria. Patients will be on standard-of-care preventative therapy for other than elevated Lp(a) CVD risk factors as per current guidelines.

Clinical diagnosis of CVD is defined as documented CAD, stroke, or PAD. A diagnosis of CAD has to be documented by any of the following:

- Angiographic evidence of  $\geq 50\%$  stenosis of 1 or more major epicardial coronary arteries.

- History of myocardial infarction documented by positive enzymes, and either symptoms of myocardial ischemia, or electrocardiogram (ECG) changes (Thygesen et al. 2012).
- History of coronary revascularization.
- Evidence of cardiac ischemia on exercise testing, or imaging study.

Patients will be evaluated for study eligibility during Screening, which takes place within 4 weeks prior to Day 1 (the first day of Study Drug administration). Patients who are determined to be eligible, based on screening assessments, will be enrolled in the study at Day 1 and randomly assigned to 1 of the 5 parallel dosing cohorts, with each cohort having a 5:1 ratio to receive ISIS 681257 or matching volume of placebo, respectively, by SC injection for up to 52 weeks.

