#### 4.5.6. Prior and Concomitant Medications

Prior and concomitant medications will be coded using the WHO Drug Dictionary (Version March 2017). Results will be tabulated by anatomic therapeutic class (ATC) and preferred term. Patients will be counted only once by ATC and preferred term. Missing and partial dates will be handled as described in [Section 3.10.3](#).

Concomitant medications will be tabulated by ISIS 681257 treatment group and pooled placebo group, where any medications that did not end prior to first dose will be included. Prior medications consist of all medication that ended prior to the first dose. If an end date is missing or the medication is ongoing, the medication will be included.

The use of prior and concomitant medications will be included in a by-patient data listing.

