### Niacin Use

Niacin use will be categorized as either Yes or No, by the use of the concomitant medication 'NICOTINIC ACID' while on-treatment.

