### PCSK9 Inhibitor Use

PCSK9i use will be categorized as either Yes or No, by the use of the following concomitant medications while on-treatment:

- ALIROCUMAB
- EVOLOCUMAB

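### The added statin, niacin and PCSK9-inhibitor subgroups are classified by drug use after randomisation, possibly after Week 25/27, so their descriptive Lp(a) tables can be biased

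*SAP*

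**What the plan says.** The addendum to SAP v1.0 adds four subgroups. Three rest on medication:

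- Intensity of Statin Therapy: High or Moderate/Low, "by the use of the following concomitant medication while on-treatment".
- Niacin Use: Yes or No, "by the use of the concomitant medication 'NICOTINIC ACID' while on-treatment".
- PCSK9 Inhibitor Use: Yes or No, "by the use of the following concomitant medications while on-treatment".

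The fourth is fixed before treatment: "The analyses by baseline Lp(a) will be categorized by quartiles, as well as >70 mg/dL versus ≤70 mg/dL". The subgroups in SAP section 3.8, age and gender, are also not affected by treatment.

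For each cohort the "treatment period is defined as the time from the first dose through one dosing interval post last dose" (text under Table 1). On duration, section 1.2.1 says: "Minimum treatment duration is 6 months, maximum treatment duration is 12 months". It also says: "The primary analysis time point is at Week 25 for patients who received every 4-week dosing (Cohorts A-C) and at Week 27" for Cohorts D and E. For concomitant medications, section 4.5.6 says "any medications that did not end prior to first dose will be included", which sets no upper time limit.

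The addendum calls the new analyses supportive. Its Supportive Efficacy Analyses section plans descriptive statistics for change and percent change in Lp(a), by treatment group and subgroup, at all visits and without imputation. It names no contrast, model, test or interaction.

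**The concern.** A subgroup is useful for reading a treatment effect when membership is settled before treatment can influence it. Here membership is settled by what happens after the first dose, with three consequences.

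- **Timing.** Nothing limits the use that counts to use before the visit being tabulated. A PCSK9 inhibitor started at Week 40 makes the patient a user in the Week 25 column.
- **Unequal windows.** Treatment closes when the last enrolled patient reaches 6 months, so early enrolees have longer to become users. Someone who stops early has a short window, and a drug started after that but before Week 25/27 is not counted.
- **Dose changes.** The statin rule gives no precedence when the dose changes, so two programmers could place the same patient in different groups.

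Readers will compare arms within these subgroups, and users with non-users within an arm. If starting, stopping or changing a lipid drug follows from on-study results or adverse events, neither comparison is clean.

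**Working it through.** **1. The plan's own figure.** Section 3.1 gives SD 20, a difference of 20 (−30 against −10), 23 per group and alpha 0.05 (two-sided per section 3.2). Noncentrality is (20/20) × √(23/2) = 3.39 on 44 degrees of freedom, so power is 91.2%, against about 90% stated. It is reproduced. The point does not depend on it; step 5 only borrows the means and SD.

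**2. Longest window.** I read on-treatment as the treatment period defined under Table 1. Last dose week = 1 + (doses − 1) × interval; the window ends one interval later.

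| Cohort | Last dose | Window ends | Weeks past primary time point | Share of 52 weeks |
|---|---|---|---|---|
| A–C | 1 + 12×4 = 49 | 53 | 53 − 25 = 28 | 54% |
| D | 1 + 25×2 = 51 | 53 | 53 − 27 = 26 | 50% |
| E | 1 + 51×1 = 52 | 53 | 53 − 27 = 26 | 50% |

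**3. Six-month window.** The per-protocol definition in section 2.1 counts 6, 13 or 26 planned doses in 6 months. A–C: 1 + 5×4 + 4 = 25. D: 1 + 12×2 + 2 = 27. E: 1 + 25 + 1 = 27. The window then ends at the primary time point. The part after the outcome thus runs from 0 to 26–28 weeks, depending on how long the patient is treated.

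**4. Statin rule.** High intensity includes atorvastatin 40–80 mg/day; Moderate/Low includes less than 40. A patient recorded at 20 and later at 40 mg/day on treatment meets both. No rule decides.

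**5. Does it bias anything?** The SAP gives no usage rates, so these are assumptions. Two million patients were simulated per scenario, half on active drug, with means −30 and −10, SD 20 and the same true difference of −20 in everyone. The added drug was given no effect on Lp(a).

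- Baseline use 5%, with starts (5%) unrelated to arm and outcome: difference −19.9 in users, −20.0 in non-users. No bias.
- Baseline use 5, 10, 20 or 50%, with 5, 10 or 20% of patients whose percent change is above −10 starting the drug: −19.0 to −21.3 in users, −19.2 to −19.8 in non-users. The largest shift is 1.3 points.
- User shares become unequal, for example 8.0% active against 14.5% placebo (baseline 5%, starts 20%).
- With baseline-defined subgroups: −19.9 to −20.2 throughout, which is simulation error.

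**6. What the tables would show.** They display arm means, not differences. With baseline share b, start probability h, arm mean μ, p the chance of a change above −10 and m the mean among those patients:

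user mean = [bμ + (1−b)hp·m] / [b + (1−b)hp].

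Active: p = 0.1587, m = −30 + 20×0.2420/0.1587 = 0.50. Placebo: p = 0.5, m = −10 + 20×0.3989/0.5 = 5.96.

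- b = 0.05, h = 0.20. Active: (−1.5 + 0.0301×0.50)/0.0801 = −18.5. Placebo: (−0.5 + 0.095×5.96)/0.145 = 0.5. The true means are −30 and −10. The difference is still −19.0. Active non-users: (−30 + 0.0801×18.5)/0.9199 = −31.0. Users and non-users in the active arm then look 12.5 points apart when they do not differ.
- b = 0.50, h = 0.05: −29.8 and −9.6, almost no shift.

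These scenarios let the start depend on the outcome itself, a strong form of dependence.

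**7. Cell size.** If 2 to 4 of 45 active patients used a rare class at baseline (an assumption), one starter adds 1/4 to 1/2, or 25–50%, to the cell. That is a change in count, not a measure of bias.

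**The case against.** The strongest reply is that little hangs on these tables. They are supportive and descriptive, with no planned subgroup estimate or test. Use carried unchanged from baseline gives the same group under either definition. The tables cover all visits, and for late visits late use is contemporaneous. Whether patients may start or change these drugs is a protocol matter, the study is double-blind, and the SAP does not say whether sites see on-study Lp(a).

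All of that stands, and it limits the point. It does not answer the timing problem in the columns up to Week 25/27, the unequal windows, or the missing rule for a changed statin dose. The last needs no assumption about bias.

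Three stronger readings are tempting and are not supported:

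- A reader might infer that the subgroup effects are biased. The text shows only that they can be; this requires starting, stopping or changing to depend on treatment or response.
- A reader might infer that a newly started lipid drug shifts follow-up Lp(a) and so mixes with the study drug's effect. No statement in the SAP supports this for these drugs. If it did happen, a baseline definition would not remove it: a patient starting at Week 10 would stay among the non-users. Only a separate listing shows it.
- A reader might infer that the trial's main conclusions are at risk. The models in sections 4.3.1 and 4.3.2 do not use these subgroups.

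**Conclusion.** The point holds as a weakness of definition worth correcting. Three of the four added subgroups use a post-randomisation variable with no cut-off at the visit tabulated, a window that differs between patients, and no rule for statin dose changes. The overhang past the primary time point is 0 to 26–28 weeks; this rests only on the SAP's dosing figures and on reading on-treatment as the defined treatment period.

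The size of any bias is not known. Under assumed response-driven starting, the between-arm difference shifts by at most 1.3 points, while user means within an arm shift by anything from under 1 to about 11 points. With starts unrelated to arm and outcome there is no bias. As planned, the tables may not be interpretable as subgroup effects. Primary and secondary inference is untouched.

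**What to change.** Classify all three subgroups by use ongoing at the first dose, with statin intensity taken from the dose on that day. This also settles the dose-change ambiguity.

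State a rule for incomplete start dates, because the imputation in section 3.10.3 was not written for this purpose:

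- A wholly missing start date becomes the first-dose date, so a strict requirement to have started earlier would lose a long-standing user.
- A start with only the day missing, in the month of the first dose, becomes the last day of that month, usually after Day 1, so a baseline user looks like a new starter.
- A start with only the year known, in the year of the first dose, becomes 1 January, so a new starter can look like a baseline user.

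List separately, by treatment group, the patients who start, stop or change these drugs before the primary time point. The on-treatment classification can stay as an additional listing, so the description of drugs actually taken is not lost.

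The SAP already works from start and end dates for concomitant medication, and the statin rule already needs the dose. The cost is revised wording in the addendum and a small amount of programming and date handling.
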